4.3 Handling of repeated and unscheduled measurements

All repeated and unscheduled measurements will be presented in the listings, where applicable. The following general rules will apply to all repeated and unscheduled measurements:

- For repeated or unscheduled measurements obtained prior to the first dose of IMP the latest reliable value (which may be scheduled or unscheduled) will be used in the calculation of descriptive statistics (ie, Screening and/or Baseline)
- For repeated or unscheduled measurements obtained at the designated Baseline visit, the latest reliable value (which may be scheduled or unscheduled) will be defined as the Baseline record if occurred prior to the first dose of IMP
- If any scheduled measurement obtained at any time point after the first dose of IMP is missing, unscheduled measurements will not be used for any missing assessment.
- See Section 10.4 for the rules applied to ECG triplicate measurements.

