8 STUDY ASSESSMENTS AND PROCEDURES

Study procedures and their timing are summarized in the Schedule of Activities (Section 1.3).

Protocol waivers or exemptions are not allowed.

Immediate safety concerns should be discussed with the sponsor (or designee - Medical Monitor at CRO) immediately upon occurrence or awareness to determine if the participant should continue or discontinue study treatment.

Adherence to the study design requirements, including those specified in the Schedule of Activities (see Section 1.3), is essential and required for study conduct.

All Screening evaluations must be completed and reviewed to confirm that potential participants meet all eligibility criteria. Screening assessments can be performed on different days throughout the Screening Period, if required. The investigator will maintain a Screening log to record details of all participants screened and to confirm eligibility or record reasons for Screening failure, as applicable.

Procedures conducted as part of the participant's routine clinical management (eg, blood count) and obtained before signing of the ICF may be utilized for Screening or Baseline purposes provided the procedures met the protocol-specified criteria and were performed within the time frame defined in the Schedule of Activities (see Section 1.3).

An Unscheduled Visit can be conducted at the discretion of the investigator (eg, due to an AE).

During the Unscheduled Visit, the following assessments will be performed:

- AE reporting
- Concomitant medications
- Review of withdrawal criteria
- Physical examination
- Vital signs
- Blood samples for PK, IgG, hematology, biochemistry, other testing such as for TB or C-reactive protein (CRP) as clinically indicated in the opinion of the investigator.

Other assessments may be performed at the discretion of the investigator.

Repeat or unscheduled samples may be taken for safety reasons or for technical issues with the samples.

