9.3 Planned efficacy/outcome analyses

9.3.1 Analysis of the primary efficacy/primary endpoint

The primary efficacy variable is the durable clinically meaningful platelet response $\geq 50 \times 10^9/L$, for at least 8 out of 12 weeks during the last 12 weeks (platelet count recorded at Week 14 to Week 25 corresponding to the response achieved following dosing at Week 13 to Week 24). Missing platelet count at any visit will be considered "worst case" and set to zero ("no platelet response") for that specific visit.

The primary and supportive analyses for the durable platelet count endpoint are detailed in [Table 9-1](#). The main intercurrent events are rescue therapy prior to Week 25 and treatment discontinuation (withdrawal from study) due to TEAEs.

Confirmatory testing of single hypotheses is based on a closed-testing procedure.

The primary analysis of the study will use a Stratified Cochran-Mantel-Haenszel test statistic.

This document cannot be used to support any marketing authorization application and any extensions or variations thereof.

PUBLIC COPY

Table 9-1: Estimands for the primary endpoint

Estimand					
Objective Clinical Category	Statistical Category	Variable/Endpoint	Population	IES^a	PLS^b (Analysis)
Primary Objective: To demonstrate clinical efficacy of rozanolixizumab as a maintenance treatment in participants with primary ITP					
Platelet Count	Primary/MCP	Durable Clinically Meaningful Platelet Response of $\geq 50 \times 10^9/L$, for at least 8 out of 12 weeks during the last 12 weeks (Week 13 to Week 25)	RS who were randomized to rozanolixizumab weekly dosing compared against those who received placebo.	A composite strategy will be used, in which participants who require rescue therapy, who experience any TEAEs leading to treatment discontinuation, discontinue prior to receiving IMP, or do not have a post-treatment assessment will be considered as nonresponders.	To test of the null hypothesis (H_0) in participants who have achieved a durable platelet count that the true common odds ratio between treatment arms is 1 (odds ratio = 1) vs the alternative hypothesis (H_a) that the odds ratio is less than 1, a Cochran-Mantel-Haenszel model adjusted for the stratification factors, namely baseline degree of thrombocytopenia (platelet count $<$ or $\geq 15 \times 10^9/L$), history of splenectomy (yes or no).

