3.2 General study level definitions

3.2.1 Analysis time points

All data will be analyzed based on the visits identified per the Schedule of Activities in the protocol.

Note: As no study participants were randomized under Protocol Amendment 3 the visit schedule and associated activities relate to those of earlier protocol versions.

Mapping to visit windows will not be applied. For Early Withdrawal visits refer to Section 3.2.3.

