4.2 Handling of dropouts or missing data

4.2.1 Handling missing data for the primary and secondary efficacy endpoints

Study participants who have not met the threshold for clinically meaningful response will be imputed as non-responders for the analysis. Missing platelet data at any visit will be considered "worst case" and set to zero ("no response") for that specific visit.

Missing data for ITP Patient Assessment Questionnaire (ITP PAQ) instrument will not be imputed.

Missing efficacy data encountered due to permanent treatment discontinuation due to TEAEs, or the receipt of rescue therapy will be considered as intercurrent events. For the primary efficacy analysis, patients with intercurrent events will be considered as non-responders.

Missing data strategy for PRO related endpoints will follow instructions indicated in each instrument.

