8.1 Statistical analysis of the primary efficacy endpoint

8.1.1 Primary analysis of the primary efficacy endpoint

The primary efficacy endpoint will be analyzed according to the following estimands' attributes:

- (1) Treatment conditions: Placebo and rozanolixizumab (please refer to section 6 Study treatments in the protocol for details)
- (2) Population: Adult Study Participants with Persistent or Chronic Primary Immune Thrombocytopenia (ITP) who fulfill the inclusion / exclusion criteria according to the protocol.
- (3) Endpoint: Durable Clinically Meaningful Platelet Response of $\geq 50 \times 10^9/L$, for at least 8 out of 12 weeks during the last 12 weeks (Week 13 to Week 25)
This endpoint includes the platelet count recorded at Week 14 to Week 25 corresponding to the response achieved following dosing at Week 13 to Week 24)
- (4) Intercurrent Events: see below.

Table 8-1: Intercurrent Events (ICE), Intercurrent Events Strategies (ICES) and Missing data Strategies for the analysis of the primary endpoint

Intercurrent Events (ICE)	ICE Strategy	Missing data strategy
a) Use of Rescue therapy from Baseline prior Week 25	A composite strategy Participants impacted by any ICE (a, b, c and d) will be considered as non-responders after the time of event.	Not applicable Section 4.2.2
b) Participants who experience any TEAEs leading to permanent treatment discontinuation		
c) Participants who discontinue prior to receiving IMP		
d) Participants who do not have any post-treatment assessment		
e) COVID-19*	A composite strategy Participants impacted by ICE (e) will be considered as non-responders at the time of event.	

* COVID-19 Impact category: Temporary discontinuation of study drug, Permanent discontinuation of study drug, Termination of study participation and Relationship to COVID-19: confirmed, suspected, general or other as recorded in the COVID-19 impact eCRF form.

(5) Population-level summary: Owing to early termination of the study, the population-level summary will be provided using descriptive statistics.

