8.2 Statistical analysis of the secondary efficacy endpoints

8.2.1 Cumulative number of weeks with Clinically Meaningful Platelet Response of $\geq 50 \times 10^9/L$ over the 24-Week treatment period (Week 1 to Week 25)

The secondary efficacy endpoint: Cumulative number of weeks with Clinically Meaningful Platelet Response of $\geq 50 \times 10^9/L$ over the 24-week treatment period will be analyzed on the RS, under the same treatment conditions and population of interest as for the primary endpoint. Note: if platelet count was assessed multiple times in a given week, Clinically Meaningful Platelet Response only needed to be observed at one timepoint during the week. ICE, ICES and population level summary will be handled as described below:

Table 8-2: Intercurrent Events (ICE), Intercurrent Events Strategies (ICES) and Missing data Strategies for the analysis of the Cumulative number of weeks with Clinically Meaningful Platelet Response of $\geq 50 \times 10^9/L$ over the 24-Week treatment period

Intercurrent Events (ICE)	ICE Strategy	Missing data strategy
a) Use of rescue therapy	A while on-treatment strategy: Participants impacted by	Participants impacted by any of the ICE will be considered as having a loss
b) Withdrawal from the study due to treatment emergent AE		

Intercurrent Events (ICE)	ICE Strategy	Missing data strategy
c) Permanent treatment discontinuation	any of the ICE will be considered as having a loss of durable platelet response at the time of the ICE occurring.	of durable platelet response at the time of the ICE occurring. Platelet data up to the start date of this ICE will be utilized in statistical analysis.
d) COVID-19*	A composite strategy: data impacted by COVID-19 will be considered as having a loss of durable platelet response at the time of the ICE occurring.	Section 4.2.2

* COVID-19 Impact category: Temporary discontinuation of study drug, Permanent discontinuation of study drug, Termination of study participation and Relationship to COVID-19: confirmed, suspected, general or other as recorded in the COVID-19 impact eCRF form.

Population-level summary: Owing to early termination of the study, the population-level summary will be provided using descriptive statistics.

8.2.2 Time to first Clinically Meaningful Platelet Response of $\geq 50 \times 10^9/L$: time from starting treatment to achievement of first response of $\geq 50 \times 10^9/L$.

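### A platelet count recorded as unscheduled cannot stand in for a missing scheduled count, so an observed response week can be scored as zero in the primary endpoint

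*SAP*

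**What the plan says.** The primary endpoint (SAP 8.1.1) requires a platelet count of at least 50×10⁹/L in at least 8 of 12 weeks, using the counts recorded at Weeks 14 to 25. Four rules decide what happens when one of those counts is missing.

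- SAP 4.3, for any time point after first dose: when the scheduled value is missing, "unscheduled measurements will not be used for any missing assessment". All such values still go into the listings.
- SAP 3.2.1: "Mapping to visit windows will not be applied". The recorded visit label therefore governs.
- SAP 4.2.1: "Missing platelet data at any visit will be considered" worst case and scored as zero. Protocol 9.3.1 has the same zero rule.
- SAP 8.1.1 and its Table 8-1 give the primary endpoint no exception for unscheduled counts.

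Protocol section 8 foresees the situation: "Repeat or unscheduled samples may be taken for safety reasons or for technical issues with the samples". Platelet counts come from local laboratories, and Protocol 8.1.1 has the date and time of each draw entered in the eCRF.

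Elsewhere the plan is more permissive. SAP 4.3 takes the latest reliable value before first dose, whether scheduled or not. Protocol 8.1.1 lets an unscheduled count confirm Response. For the cumulative-weeks endpoint, SAP 8.2.1 says of a week with several counts that "Clinically Meaningful Platelet Response only needed to be observed at one timepoint during the week".

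**The concern.** Worst-case imputation is meant for values nobody knows. Here the value was measured, appears in the listings, and is then replaced by zero in the summary, so listing and summary can disagree for the same participant and week. The zero rule comes from the protocol. The bar on using an unscheduled count appears only in SAP 4.3, in a general rule not written with the weekly platelet endpoint in mind.

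What is at stake is the reported durable-response proportion. Only counts at or above the threshold can be harmed, so the error has one direction, and its absolute size is larger in an arm with more responders.

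There is also a gap between endpoints. SAP 8.2.1 does not say whether its one-count-per-week note lets an unscheduled count serve when the scheduled one is missing. Two programmers could reasonably score the same week differently for the primary and the cumulative-weeks endpoints.

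**Working it through.** **Step 1: the rule chain for one week.** Let X be a local count taken close to a scheduled visit in Weeks 14 to 25, recorded as unscheduled, with the scheduled count missing.

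1. SAP 4.3: X may not replace the missing value.
2. SAP 3.2.1: X is not moved to the scheduled visit.
3. SAP 4.2.1: the scheduled value becomes 0.
4. SAP 8.1.1: 0 < 50, so the week does not count.

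If X ≥ 50, a response week is lost. If X < 50, the week was a non-response anyway. The scored number of weeks can therefore only fall.

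**Step 2: effect on a participant.** With T true response weeks and k of them zeroed this way, the score is S = T − k, and a responder needs S ≥ 8.

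- T = 8, k = 1: S = 7, non-responder.
- T = 12, k = 4: S = 8, still a responder.
- T = 12, k = 5: S = 7, non-responder.

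**Step 3: effect on an arm.** SAP 2.4 and 3.9 give 33 randomized participants. Assuming the 2:1 allocation produced 22 and 11, one reclassified participant moves the rate by 1/22 = 4.5 points (rozanolixizumab) or 1/11 = 9.1 points (placebo).

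**Step 4: an illustrative average.** The documents give no rate of missed and redrawn counts, so this step rests on assumptions. The starting point is the plan's own rates of 0.45 and 0.05 (SAP 2.4). As a check on those inputs, exact enumeration of Fisher's test with n = 40 and n = 20 at one-sided 0.025 gives 93.0% power, against 93% in SAP Table 2-1.

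Model: T follows a beta-binomial on 12 weeks, with parameters a and b chosen so that P(T ≥ 8) equals 0.45 or 0.05. A share m of scheduled counts is missed and redrawn as unscheduled, so S given T is binomial(T, 1 − m). The sum a + b controls how alike one person's weeks are; smaller means more alike.

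| a + b | Active scored, m = 5% | Active scored, m = 10% | Placebo scored, m = 5% |
|---|---|---|---|
| 0.5 | 0.4352 | 0.4164 | 0.0471 |
| 1 | 0.4265 | 0.3984 | 0.0453 |
| 2 | 0.4157 | 0.3768 | 0.0433 |

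At m = 5% the active rate loses 0.45 − 0.4352 = 1.5 points to 0.45 − 0.4157 = 3.4 points. The placebo rate loses 0.05 − 0.0471 = 0.3 to 0.05 − 0.0433 = 0.7 points. At m = 10% the active loss is 3.4 to 7.3 points. For the abandoned 60-participant test, power at m = 5% would fall from 93.0% to between 90.6% and 92.0%.

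**The case against.** Several points on the other side stand.

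- **Labelling.** The post-dose sentence in SAP 4.3 names only unscheduled values, whereas the section heading and the pre-dose rules also name repeated ones. A failed sample redrawn and entered under the scheduled visit counts normally. Nothing in the documents requires such a redraw to be labelled unscheduled.
- **Window.** A reader might point to the ±2 days in Protocol Table 1-4 and say that in-window redraws are being thrown away. That table is the Amendment 3 schedule. SAP sections 1 and 3.2.1 say that nobody was randomized under it and that earlier schedules apply; those schedules are not in the documents.
- **SAP 8.2.1.** A reader might infer a contradiction with the primary endpoint. The note covers weeks with several counts, which scheduled visits alone can produce: Baseline and Day 3 both fall in Week 1. It does not say that an unscheduled count fills a gap. This is an ambiguity to settle, not an established conflict.
- **Deliberate choice.** The zero rule is pre-specified and conservative, and the protocol's amendment history attributes it to a regulator's request. Excluding unscheduled counts also guards against sampling triggered by clinical events. That worry is largely met if such a count is used only when the scheduled one is missing, and because Table 8-1 already makes participants non-responders after rescue therapy.
- **Consequence.** SAP 3.9 reduces efficacy to description, and the observed values remain visible in the listings.

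None of this removes the case where the nearby count carries an unscheduled label.

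**Conclusion.** The point holds at the level of the week: a known count of 50×10⁹/L or more, recorded as unscheduled when the scheduled count is missing, is scored as no response. The direction is certain, downward or nil. The size is not: it depends on how often this happened and how sites labelled redraws, and the documents report neither.

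Two stronger readings are not supported. One is that a single redraw makes the participant a primary non-responder; four of the 12 weeks may fail, so this is true only at exactly 8/12. The other is a large average loss. If weeks are treated as independent with a common weekly probability of 0.6, 0.7 or 0.8, zeroing 5% of counts lowers P(at least 8 of 12) from 0.438 to 0.356, 0.724 to 0.627 and 0.927 to 0.862, drops of 6.5 to 9.7 points. Nothing in the documents supports independence or the 5%. Allowing for similarity within participants at the planned 0.45 rate gives about 1.5 to 3.4 points for the same 5%, also only an illustration, since 0.45 was the design rate for weekly dosing and the analysed participants had bi-weekly dosing.

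No hypothesis test is affected. What remains is a small, avoidable downward error in a reported primary result, where one participant is worth about 4.5 or 9.1 points under the assumed 22:11 split.

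**What to change.** Add a platelet exception to SAP 4.3:

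- If the scheduled count is missing, use the repeat or unscheduled local count closest to the nominal day and within the visit window of the protocol version under which the participant was treated.
- Set the visit to zero only if no such count exists.
- Where a scheduled count exists, it stands for the primary endpoint and extra counts are ignored.

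State in SAP 8.1.1 and 8.2.1 how this rule applies, so that the primary and cumulative-weeks endpoints treat a missing scheduled count the same way. The intercurrent-event rules, including non-response after rescue therapy, would continue to apply.

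The cost is some SAP wording and a few lines of programming, with no new data. Draw dates must be checked against the applicable window, and the reported rate becomes slightly less conservative.

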4.4 Handling and definition of the Corticosteroid (CS) prednisone equivalent dose

For the purposes of further analysis and tabulations, all corticosteroid doses (including both prior and concomitant corticosteroids taken for any indication) will be converted to prednisone equivalent doses. The conversion table for systemic corticosteroids is presented in Table 4-2.

Systemic corticosteroids are those with a route of administration of oral, intravenous, or intramuscular. All others (including topical, ocular, nasal, subcutaneous, intraarticular, etc.) will be considered non-systemic steroids which will have a prednisone equivalent dose = 0mg/day.

Budenoside is considered non-systemic even if taken orally and will always be assigned a prednisone equivalent dose = 0mg/day.

The prednisone equivalent dose will be included in the listing.

For example, if the total daily dose of triamcinolone is 8mg, the equivalent total daily dose of prednisone will be 10mg. If a new corticosteroid is reported that is not in Table 4-2, the appropriate prednisone equivalent conversion will be determined and the prednisone equivalent dose will be included in a separate systemic corticosteroids concomitant medication listing.

If medications are available in [REDACTED] which are not in table below, then the dose equivalent to 5mg/day Prednisone will be provided by the physician for this new system CS and the TFL footnote will be updated with this information for the newly identified CS

Table 4-2: Prednisone equivalent doses of systemic corticosteroids/steroids

Corticosteroids /Steroids	Dose equivalent to 5mg/day Prednisone
Cortisone	25
Hydrocortisone	20
Deflazacort	6.5
Prednisone	5
Prednisolone	5
Methylprednisolone	4
Triamcinolone	4
Dexamethasone	0.75
Betamethasone	0.6

Notes:

- All non-systemic corticosteroids (including topical, ocular, nasal, subcutaneous, intra articular, etc.) will be assigned a prednisone equivalent dose = 0 mg/day.
- ATC2 Term = "C01AC06 CORTICOSTEROIDS FOR SYSTEMIC USE, [REDACTED]"

4.5 Interim analysis and data monitoring

4.5.1 Data Monitoring

An external IDMC will be established to review the safety data at predefined intervals and ad hoc as needed, should emerging safety concerns arise during the study. The IDMC will consist of members independent from UCB. Study enrollment will not be halted during planned IDMC review of the safety and efficacy data. The IDMC will have the possibility to unblind the data. Details of the IDMC composition, processes, and responsibilities will be documented in the IDMC charter. One IDMC is planned for both pivotal studies (TP0006 and TP0003), where the safety data will be initially presented unpooled, ie, data from each study will be reviewed separately. Key safety data may be pooled at the discretion of the IDMC for protection of all study participants if warranted. The first IDMC meeting for the review of safety data is planned to occur after approximately 15 participants have received 3 doses of IMP in TP0003. The

intervals for planned IDMC meetings are included in the section 4.1.2.1 in the TP0003/TP0006 Independent Data Monitoring Committee Charter. The study will be put on hold if any of the following occurs:

- The IDMC judges it necessary for medical or safety reasons and
- The sponsor or its designee judges it necessary for medical, safety, regulatory, or any other reasons consistent with applicable laws, regulations and Good Clinical Practice.
- An ad hoc IDMC meeting for the review of safety data is planned to occur if one of the stopping rules is met:
 - **US & Canada Rule:** Three participants experience any serious adverse event (SAE) within the first 15 study participants who have received at least one dose of IMP across TP0003 and TP0006, unless the SAE is clearly unrelated to the study drug.
 - **Rest of World Rule:** Three participants experience an SAE of the same type within the first 15 study participants who have received 3 doses of IMP across TP0003 and TP0006, unless the SAE is clearly unrelated to the study drug.

4.5.2 Interim analyses:

The interim analysis planned for this study under previous protocol versions was removed from Protocol Amendment #3.

